6.2 Investigator responsibilities

SAEs should be notified to CCTU immediately and no later than **24 hours** after the CFC staff becomes aware of the event by email to the HWFinEL trial team using the trial specific SAE form.

6.2.1 Assessment of AEs

6.2.1.1 Seriousness

When an AE occurs, the researcher responsible for the care of the participant must first assess whether or not the event is serious using the definition given in Table 3. If the event is classified as 'serious' then an SAE form must be completed and CCTU (or delegated body) notified immediately (within 24 hours).

6.2.1.2 Causality

The researcher must assess the causality of all serious events in relation to the trial intervention using the definitions in Table 4. There are five categories: unrelated, unlikely, possibly, probably, and definitely related. If the causality assessment is unrelated or unlikely to be related, the event is classified as an '**unrelated SAE**'. If the causality is assessed as possibly, probably or definitely related, then the event is classified as a '**related SAE**'.

Table 4: Assigning Causality

Relationship	Description
Definitely	There is clear evidence to suggest a causal relationship and other possible contributing factors can be ruled out
Probably	There is evidence to suggest a causal relationship and the influence of other factors is unlikely
Possibly	There is some evidence to suggest a causal relationship (e.g., because the event occurs within a reasonable time after administration of the trial intervention). However, the influence of other factors may have contributed to the event (e.g., the participant's clinical condition, other concomitant events)
Unlikely	There is little evidence to suggest that there is a causal relationship (e.g., the event did not occur within a reasonable time after administration of the trial intervention). There is another reasonable explanation for the event (e.g., the participant's clinical condition, other concomitant event)
Unrelated	There is no evidence of any causal relationship

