1.4 Benefit Risk Assessment

The intervention plans to evaluate if there are additional benefits from receiving welfare benefit advice. There are no anticipated risks involved in participating in the intervention.

It is expected that the only risks of participation in the HWFinEL trial may be the possible unease or discomfort resulting from answering sensitive questions from the questionnaires/interviews pertaining to the participant's life. Contact information will be available for appropriate consultation should any of the material become distressing. The researchers will be alerted to scores of 10 or higher recorded on the mental health questionnaires (PHQ-8 and GAD-7) and this information will be shared with a health professional if it warrants further evaluation or support.

2 Selection of Sites/Investigators

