5.6 Completion of Protocol Follow-Up

Participants will complete protocol follow-up upon the completion of the questionnaire/and the in-depth interview at 6 months (if they consent to take part in this).

6 Safety reporting

This trial is very low risk as the trial intervention groups are non-invasive (i.e. money advice being offered). As such, serious adverse events are not anticipated in the HWFInEL trial; if any Serious Adverse Events (SAEs) occur to a participant during the trial, these will be recorded and appropriate action taken (i.e. intervention discontinuation or withdrawal, as deemed appropriate by the researchers).

SAEs that are **related** to the study (i.e. they resulted from any of the research procedures) and **unexpected** will be reported to the REC using the relevant documentation.

These should be sent within 15 days of the Chief Investigator becoming aware of the event.

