6.2.1.4 Expectedness

If there is at least a possible involvement of the trial intervention (or comparator), the expectedness of the event should be assessed by the CCTU delegated clinical reviewer. The Sponsor has the overall responsibility for determination of expectedness.

Table 6: Expectedness

Expectedness	Description
Expected	An adverse event which is consistent with the information about the trial procedures/intervention defined in this protocol
Unexpected	An adverse event which is not consistent with the information about the trial procedures/intervention defined in this protocol

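### The protocol gives four different answers to what a serious adverse event must be related to, and its only causality step leaves out the questionnaires and interviews, the source of the only risk it names

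*Protocol*

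**What the plan says.** Section 1.4 (Benefit Risk Assessment) says of the advice service: "There are no anticipated risks involved in participating in the intervention". It then says that "only risks of participation in the HWFinEL trial may be the possible unease or discomfort resulting from answering sensitive questions from the questionnaires/interviews".

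Section 6 (Safety reporting) requires SAEs that are both related and unexpected to be reported to the REC. It explains related as meaning that "they resulted from any of the research procedures".

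Section 6.2.1.2 (Causality) gives the only procedure for deciding relatedness: "The researcher must assess the causality of all serious events in relation to the trial intervention using the definitions in Table 4". On the outcome it says: "If the causality assessment is unrelated or unlikely to be related, the event is classified as an" unrelated SAE. The three stronger categories give a related SAE. In Table 4, the Possibly row offers as an example of evidence "because the event occurs within a reasonable time after administration of the trial intervention"; the Unlikely row has the mirror image.

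Section 6.2.1.3 asks for severity grading of related SAEs only.

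Section 6.2.1.4 (Expectedness) opens: "If there is at least a possible involvement of the trial intervention (or comparator), the expectedness of the event should be assessed". Table 6 in that section then judges expectedness against what the protocol says about both the trial procedures and the intervention.

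**The concern.** Relatedness is one concept in the reporting chain, so every step should test it against the same thing. Here the step that produces the label uses the narrowest object, the trial intervention, and so omits the one source of risk that section 1.4 identifies. Section 4.5 lists the intervention, follow-up and data collection as separate things to which a participant consents, so the questionnaires cannot easily be read into the word intervention.

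At stake is the classification of any serious event that a questionnaire or interview brings about. If it is labelled unrelated, the later steps that depend on the label do not start. A final statement that no related SAEs occurred would then partly reflect the wording of 6.2.1.2 rather than what the research procedures did.

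**Working it through.** No calculation decides this point. The check sets the passages side by side and follows one event through them.

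| Place in the protocol | What the event is tested against | What the step decides |
|---|---|---|
| Section 6 | any research procedure | whether an unexpected SAE goes to the REC |
| 6.2.1.2, lead sentence | trial intervention | the related or unrelated label |
| 6.2.1.3 | the label from 6.2.1.2 | whether severity is graded |
| 6.2.1.4, first sentence | intervention or comparator | whether expectedness is assessed |
| Table 6 in 6.2.1.4 | trial procedures and intervention | expected or unexpected |

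Take a participant admitted to hospital after a distress reaction to a questionnaire.

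1. Seriousness (6.2.1.1): the admission makes the event serious. An SAE form is completed and CCTU is told within 24 hours. This comes before causality.
2. Causality (6.2.1.2, literal reading): the advice played no part, so the label is unrelated SAE.
3. Severity (6.2.1.3): not graded, because the event is not labelled related.
4. Expectedness (6.2.1.4): not triggered, because neither intervention nor comparator is possibly involved.
5. REC reporting through these steps: the event was never found related and unexpected, so nothing sends it on.
6. REC reporting through section 6 alone: the event resulted from a research procedure, so it is related and is reportable if unexpected.

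Steps 5 and 6 can give opposite results for the same event, and the protocol does not say which governs.

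The conflict is sharpest at baseline. Sections 1.3 and 8.2.5 place randomisation after the baseline measures, and Table 2 schedules an SAE review at the baseline visit. An event set off by the baseline questionnaire can therefore precede allocation, when there is no intervention for it to be related to.

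On size, the planned number meeting the questionnaires is 1153, at baseline and again at 6 months, with 45 interviewed. Under 1:1 allocation, 1153 / 2 = 576.5, so about 577 are allocated to the advice. These are counts of people exposed, not of events misclassified. The protocol gives no SAE rate from which to derive the latter.

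**The case against.** Several points on the other side stand, and they limit the conclusion.

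- A reader might infer that such an event never reaches the REC. The document does not support that. Section 6 is itself the REC reporting rule and covers events from any research procedure; nothing says 6.2.1.2 overrides it. The supportable statement is that the event might not be reported.
- A reader might also infer that the safety system cannot detect this harm. That fails too. Sections 6.2 and 6.2.1.1 require notification to CCTU within 24 hours, and 6.2.1.1 does so for any serious event before causality is considered. Table 2 schedules SAE review at baseline, in both arms and at 6 months, and section 16.3 gives the TSC a data monitoring and ethics function. The event is seen; it may carry the wrong label.
- The named risk is unease or discomfort, which is not in itself serious. Section 1.4 gives it its own safeguards: contact information, and alerts to the researchers for PHQ-8 or GAD-7 scores of 10 or higher.
- REC reporting also needs the event to be unexpected. Distress no worse than section 1.4 describes would probably count as expected under Table 6. Only an event going beyond that description could be reportable, although as worded 6.2.1.4 never reaches the question.
- Table 4 mentions the intervention only in examples, in two of five rows. The restriction rests on the lead sentence of 6.2.1.2.
- It is tempting to say that control-arm events can never be classed as related. The text does not fix that: the protocol summary lists both arms under interventions, and Table 2 lists the control post card there. On that wider reading the comparator is covered. The questionnaires and interviews still are not, because they belong to neither arm's intervention.

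What remains after all this is the mismatch between section 6 and the steps meant to carry it out.

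**Conclusion.** The protocol contradicts itself on what an SAE must be related to. Followed literally, 6.2.1.2 and 6.2.1.4 classify a serious event caused by a questionnaire or interview in a way that conflicts with section 6, in either arm and before allocation. The consequence is a wrong label, no severity grading, no expectedness review and a possible failure to report to the REC.

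This rests on two assumptions: that researchers apply the lead sentence of 6.2.1.2 as worded, and that no other trial document corrects it. The practical size is probably small, since section 6 does not anticipate SAEs, and it cannot be put as a number. The point is still worth correcting, because the wording misses the only risk the protocol itself names.

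**What to change.** Reconcile the passages by bringing the working steps into line with the definition section 6 already contains:

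- In the lead sentence of 6.2.1.2, have causality assessed against the trial intervention, the comparator or any research procedure, in both arms.
- Reword the timing examples in the Possibly and Unlikely rows of Table 4 to match.
- Widen the first sentence of 6.2.1.4 (Expectedness) in the same way, so that its trigger fits Table 6.
- Record for each SAE which of these it is attributed to, if the SAE form, which is not among the documents, does not already do so.

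The cost is wording in three places and at most one field on a form. A few more events may be classed as related and go through review.

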6.2.1.3 Severity or Grading of Adverse Events

The severity of all 'related' SAEs in this trial should be graded using the toxicity gradings in the Common Terminology Criteria for Adverse Events (CTCAE) Version 5.0 (2017). Grades for SAEs according to the CTCAE are as per Table 5 (next page).

Table 5: Toxicity Gradings for Adverse Events

Grade	Description
1	Mild; asymptomatic or mild symptoms; clinical diagnostic observations only; intervention not indicated
2	Moderate; minimal, local or non-invasive intervention indicated; limiting age-appropriate instrumental activities of daily living (ADL)*
3	Sever or medically significant but not life threatening; hospitalisation or prolongation of hospitalisation indicated; disabling; limiting self-care ADL**
4	Life threatening consequences; urgent intervention required
5	Death related to AE or AR

*Instrumental ADL refer to preparing meals, shopping for groceries or clothes, using the telephone, managing money etc.

** Self-care AD refer to bathing, dressing and undressing, feeding self, using the toilet, taking medications and not bedridden.

Where no specific grading criteria exist for an event, the event should be graded according to the CTCAE general guidelines.

6.2.1.4 Expectedness

If there is at least a possible involvement of the trial intervention (or comparator), the expectedness of the event should be assessed by the CCTU delegated clinical reviewer. The Sponsor has the overall responsibility for determination of expectedness.

Table 6: Expectedness

Expectedness	Description
Expected	An adverse event which is consistent with the information about the trial procedures/intervention defined in this protocol
Unexpected	An adverse event which is not consistent with the information about the trial procedures/intervention defined in this protocol

6.2.1.4 Urgent Safety Measures

The CCTU or Chief Investigator may take appropriate urgent safety measures in order to protect research participants against any immediate hazard to their health or safety. These should be reported to the REC within 3 days via email notification.

7 Quality Assurance & Control

7.1 Risk Assessment

The Quality Assurance (QA) and Quality Control (QC) considerations for the HWFinEL trial are based on the standard CCTU Quality Management Policy that includes a formal Risk

Assessment, and that acknowledges the risks associated with the conduct of the trial and proposals of how to mitigate them through appropriate QA and QC processes. Risks are defined in terms of their impact on the rights and safety of participants; project concept including trial design, reliability of results and institutional risk; project management; benefit risk of the trial (see section 1.4); and other considerations.

QA is defined as all the planned and systematic actions established to ensure the trial is performed and data generated, documented and/or recorded and reported in compliance with the principles of GCP and applicable regulatory requirements. QC includes the operational techniques and activities performed within the QA system to verify that the requirements for quality of the trial related activities are fulfilled.

The HWFinEL Risk Assessment has been reviewed by the CCTU's Quality Management Group (QMG).

7.2 Central Monitoring at CCTU

CCTU staff will review data and other information provided by investigators to identify trends, outliers, anomalies, protocol deviations and inconsistencies. The frequency and type of central monitoring will be detailed in the HWFinEL QMMP.

7.3 Monitoring

The frequency, type and intensity of routine on-site monitoring and the requirements for triggered on-site monitoring will be detailed in the HWFinEL QMMP, including any provision for remote or self-monitoring. The QMMP will detail the procedures for review and sign-off of monitoring reports. In the event of a request for a trial site inspection by any regulatory authority UCL CCTU must be notified as soon as possible.

7.3.1 Direct access to Participant Records

CFCS must agree to allow trial-related monitoring, including audits, and EC review, by providing access to source data and other documents as required. Participant consent for this must be obtained as part of the informed consent process for the trial.

7.3.2 Confidentiality

CCTU plan to follow the principles of the UK DPA regardless of the countries where the trial is being conducted.

Participant's data will be collected and kept securely. Confidentiality of participant's personal data is ensured by not sharing participant names and other personally identifiable information on CRFs and receiving only pseudonymised data. Pseudonymised data will be stored in the REDCap database (separate to the administrative database). At trial enrolment, participants will be allocated a Participant Identification Number (PIN), which will be used on all trial related paperwork sent to UCL CCTU and in the trial database. Any documents (e.g. screening and enrolment logs) linking PIN to participant's personally identifiable information will be kept securely at the CFC; only redacted copies will be sent to Sponsor if requested.

Copies of participant's trial data will be kept at the participating CFC in a secure location with restricted access. Unless working at a site, CCTU staff will only have access to the data collected on the trial CRFs (i.e. they will not have access to any other personal data) and

applicable source data, moreover only staff working on the trial will have access to these data. Where paper copies of CRFs have been sent to CCTU (due to central database unavailability, e.g., system updates, system failure), all CCTU copies of CRF data on paper are stored securely in locked filing cabinets at the UCL CCTU office. Data stored electronically are held on secure servers, that have restricted access.

The informed consent form will carry the participant's name and an appropriate signature; these will be retained on the REDCap database as it will be completed electronically with restricted access. The consent forms will only be accessed by UCL CCTU staff for purposes of monitoring the consent procedure.

7.4 Source Data

The investigator/institution should maintain adequate and accurate source documents and trial records that include all pertinent observations on each of the site's trial participants. Source data are contained in source documents and are defined by EU guidelines as all information in original records that are used for the reconstruction and evaluation of the clinical trial. Source documents are the first place where the source data are recorded. These can include hospital records, clinical and office charts, laboratory notes, X-rays, questionnaires, source data worksheets and pharmacy dispensing records.

Source data should be attributable, legible, contemporaneous, original, accurate, and complete. Changes to source data should be traceable, should not obscure the original entry, and should be explained if necessary (e.g., via an audit trail). Each data element should only have one source.

For this trial, the majority of datapoints will be recorded directly into CRFs/eCRFs and therefore the CRF/eCRF will be regarded as source data. However, a minority of datapoints will be recorded in the participant's notes. In such cases, the participants notes will be regarded as source data. The location of each datapoint will be detailed in the HWFinEL Data Management Plan.

Paper CRFs will be provided to the CFC to be used as a back-up for instances when the EDC is unavailable (e.g., system updates, build maintenance, system failures). Paper CRFs will be provided to CFCs and should only be used as a temporary measure until the EDC is restored.

A Source Data Agreement will be put in place as part of the activation process with each CFC. This will define the source documents and the data therein, together with location of these source documents and any applicable plans for transmission of source data between the CFC and CCTU.

All trial data will be verifiable from source documents, which may include CRFs/eCRFs, and paper notes.

7.5 Data Collection and Transfer Methods

Each CFC will be allocated a unique site code and enrolled participants will be given a unique randomisation Participant Identification Number (PIN), which will be used for all data collection

forms. At the point of screening, the participants will be assigned a unique Screening ID number in sequential order following consent.

The preferred method of data collection is direct online entry of data onto the Electronic Data capture (EDC) system sponsor central database REDCap. Paper CRFs can be used as an intermediary (i.e. as CRF worksheets, if CFCs wish to) between the source data and the EDC, however, ultimately all data are to be entered into the EDC.

Trial specific CRFs will be designed by the HWFinEL trial team. The approved CRFs will be provided to CFCs/used by UCL Researchers.

Training on data collection, secure data transfer and storage for CFC staff listed on the delegation of responsibilities log will be provided at the site initiation meeting or prior to green light activation.

7.6 Data Management

Data will be collected at the time-points indicated in the Schedule of Assessments Participant Timeline (Section 5.2). Data will be entered remotely under the assigned unique PINs onto the central database. The database software provides a number of features to help maintain data quality, including maintaining an audit trail, allowing custom validations on data, allowing users to raise data query requests, and search facilities to identify validation failure and missing data.

Data collection, data entry, data queries (raised by a member of the HWFinEL trial team), data coding and database lock(s) will be conducted in line with the CCTU Standard Operating Procedures (SOPs) and trial-specific Data Management Plan.

The database will be password protected and only accessible to members of the HWFinEL trial team at CCTU/UCL Researchers, delegated CFC staff and external regulators if requested. Database users will only be granted permissions to use the database functionality appropriate to their role in the clinical trial. The servers are protected by firewalls and are patched and maintained according to best practice. The physical location of the servers is protected by CCTV and security door access.

Identification logs, screening logs and enrolment logs will be completed and held securely at the CFC/UCL CCTU.

All data will be handled in accordance with the Data Protection Act 2018, the EU General Data Protection Regulation (GDPR) 2016 (and subsequent updates and amendments).

7.7 Data Storage

Trial data will be stored in a database created specifically for the HWFinEL trial.

The database is created using REDCap, hosted by UCL. The data are stored on secure, GDPR-compliant, cloud-based servers held within the UK:

<https://projectredcap.org/software/mobile-app/privacypolicy/>

The randomisation service is hosted by Sealed Envelope LTD. The data are stored on a secure, GDPR-compliant, cloud based servers held within the EEA/EU:

<https://www.sealedenvelope.com/security/>

The identification, screening and enrolment logs, linking personally identifiable information to the PIN, will be held by the CFC and in the separate secure admin database. This will either be held in written form in a locked filing cabinet or electronically in password protected form on REDCap Data Safe Haven. After completion of the trial the identification, screening and enrolment logs will be stored securely by the sites for 5 years after trial closure unless otherwise advised by CCTU.

